10.2 Recording and Reporting AEs and SAEs

Adverse events (AEs) will be evaluated and documented by the clinical staff and investigators throughout inpatient hospitalizations and each outpatient visit. CRAs are responsible for reviewing documentation related to AEs and entering directly into CRIS

protocol-specific database. The data to be recorded are 1) the event description, 2) the NCI CTCAE v4.0 code and grade, 3) the onset date, 4) the resolution date (or ongoing), 4) action taken for event, 5) patient outcome 6) relationship of AE to protocol treatment/interventions, 7) if AE was expected or unexpected, and 8) comments, if applicable.

AEs that are classified as serious, unexpected, and at least possibly related will be notated as such in the database as “SAEs”.

Attribution of an Adverse Event

Not related- The lack of a temporal relationship of the event to study treatment makes a causal relationship not reasonably possible, or other drugs, therapeutic interventions or underlying conditions provide a sufficient explanation.

Unlikely related- The temporal relationship of the event to study treatment makes a causal relationship reasonably unlikely, and other drugs, therapeutic interventions or underlying conditions may not provide sufficient explanation for the observed event.

Possibly related- The temporal relationship of the event to study treatment makes a causal relationship reasonably possible, and the event is more likely explained by exposure to the study treatment than by other drugs, therapeutic interventions or underlying conditions.

For the purpose of safety analyses, all AE’s that are classified as unlikely or possible will be considered treatment-related events.

These events will be reported expeditiously to the St. Jude IRB within the timeframes as described above. Cumulative summary of Grades 2-5 events will be reported as part of the progress reports to IRB at the time of continuing review. Specific data entry instructions for AEs and other protocol-related data will be documented in protocol-specific data entry guidelines, which will be developed and maintained by study team and clinical research informatics.

Patients with abnormal blood counts due to bone marrow involvement by disease (i.e. all leukemia patients and lymphoma patients with bone marrow involvement) will be considered non-evaluable for hematological toxicities.

The study team will meet regularly to discuss AEs (and other study progress as required by institutional DSMP). The PI will review Adverse Event reports generated from the research database, and corrections will be made if applicable. Once the information is final the PI will sign and date reports, to acknowledge his/her review and approval of the AE as entered in the research database.

10.3 Process for Reporting Adverse Events From and To Collaborating Sites

Adverse events from collaborating sites will also be reviewed by the PI and discussed in study team meetings as described above. SAE reports from collaborating sites for AEs

that are serious, unexpected, and at least possibly related to protocol treatment or interventions will be reported to site IRB and the St. Jude IRB within the reporting requirements described above. The PI will determine if this is an event that will need to be reported expeditiously to all participating sites, considering the following criteria:

- Is the AE serious, unexpected, and related or possibly related to participation in the research?
- Is the AE expected, but occurring at a significantly higher frequency or severity than expected?
- Is this an AE that is unexpected (regardless of severity that may alter the IRB's analysis of the risk versus potential benefit of the research *and*, as a result, warrant consideration of substantive changes in the research protocol or informed consent process/document?

With the submission of the "Reportable Event" in St. Jude TRACKS application, the PI will indicate if all sites should be notified to report to their IRBs, and if the protocol and/or consent should be amended (consent will be amended if event is information that should be communicated to currently enrolled subjects).

Generally, only events that warrant an amendment to the protocol and/or consent will be reported expeditiously to all sites. However, any event may be reported expeditiously to all sites at the discretion of the PI.

A cumulative summary of Grade 2-5 AEs and expected/unrelated deaths that occur more than 30 days after protocol treatment will be reported to all sites with study progress report at the time of continuing review.

For collaborating sites: Serious AND unexpected events are to be reported to the St. Jude PI ([name]) within 48-72 hours via fax or email.

Unexpected deaths must be reported to the St. Jude PI via phone call or email within 24 hours of the event. A written report must follow.

All correspondence and reports must also be sent by email to the **SELHEM study team**.

[name], PhD
Department of Oncology
Leukemia/Lymphoma Division
St. Jude Children's Research Hospital
[name]
[name]
Phone: [REDACTED]
FAX: [REDACTED]
Email: [REDACTED]
Email: [REDACTED]

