10.1.1 Reporting to Karyopharm

In addition to reporting to the FDA, St. Jude will forward completed SAE form to representatives of the Karyopharm Team:

[REDACTED]

It is the responsibility of St. Jude, the sponsor, to collect and document required information regarding Adverse Events (AEs) in accordance with all applicable laws and regulations.

St. Jude shall be responsible for ensuring that reports of Serious Unexpected Suspected Adverse Reactions (SUSARs) are prepared and submitted to the appropriate Regulatory Authorities, Competent Authorities, Institutional Review Boards (IRBs) and Ethics Committees (ECs) in accordance with applicable regulations and legislation.

For all SUSARs, St. Jude is responsible for providing a copy of the regulatory report (to include a MedWatch or CIOMS forms) to Karyopharm Therapeutics at [REDACTED] promptly - to mean as soon as is possible, and not more than 15 days from becoming aware of the event.

In addition to SUSAR reporting to Karyopharm, St. Jude is responsible for providing 6-month Adverse Reaction Reports (all AEs assessed as causality related to Karyopharm investigational product) to Karyopharm Therapeutics at [REDACTED] throughout the duration of the study. These reports are to contain listings of non-serious (expected or unexpected) adverse reactions and serious or non-serious expected adverse reactions which were collected during the 6-month report cycle.

St. Jude is responsible for obtaining any additional follow-up information regarding safety reports, upon request from Karyopharm.

KARYOPHARM THERAPEUTICS will inform St. Jude regarding any SUSAR detected in other clinical studies, ISTs, or compassionate use as promptly as is possible upon becoming aware of same.

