11.2 Study Monitoring

The Clinical Research Monitor will track accrual continuously and verify 100% of all data points on all study participants *quarterly* to assess overall study conduct, Human Subjects Protections, and the accuracy of database entries. Essential regulatory documents and all study documents including medical records, electronic media, database entries, study worksheets, and case report forms will be reviewed for recording and reporting of Adverse Events/Serious Adverse Events (SAEs) to include type, grade, attribution, duration, timeliness and appropriateness. Study documents are also reviewed for participant status, eligibility, the informed consent process, demographics, staging, study objectives, subgroup assignment, treatments, evaluations, responses, participant protocol status, off-study and off-therapy criteria, and for all other specifics as detailed in the protocol. The Monitor will generate a formal report which is shared with the Principal Investigator (PI), study team and the Internal Monitoring Committee (IMC).

Monitoring may be conducted more frequently if deemed necessary by the CPDMO and/or the IMC.

Continuing reviews by the IRB and CT-SRC will occur at least annually. In addition, SAE reports in TRACKS (Total Research and Knowledge System) are reviewed in a timely manner by the IRB/ OHSP.

Source document verification of eligibility for all SJCRH cases will be performed within two weeks of completion of enrollment. This will include verification of appropriate documentation of consent. Monitoring of timeliness of serious adverse event reporting will be done as events are reported in TRACKS.

Monitoring of this protocol is considered to be in the high-risk 2 category (HR-2). The Monitoring Plan is outlined in a separate document from this protocol, but has been submitted for review and approval by the Clinical Trials Scientific Review Committee and the Institutional Review Board.

St. Jude affiliates and domestic collaborating study sites will be monitored on-site by a representative of St. Jude at intervals specified in the Data and Safety Monitoring Plan. International collaborators will be monitored by a Contract Research Organization (CRO), or other mechanisms according to the study-specific monitoring plan.

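### Section 10.3 names serious, unexpected, possibly related events as a ground for prompt notice to all sites, then sets a default that need not send them, with no time limit

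*Combined protocol and SAP*

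**What the plan says.** Section 10.3 governs the flow of adverse event information from the sponsor to the collaborating sites. It first gives the PI a case-by-case decision: "The PI will determine if this is an event that will need to be reported expeditiously to all participating sites". The first of three criteria to consider is: "Is the AE serious, unexpected, and related or possibly related to participation in the research". When the event is entered in TRACKS, "the PI will indicate if all sites should be notified to report to their IRBs". The section then states the default: "Generally, only events that warrant an amendment to the protocol and/or consent will be reported expeditiously to all sites". The next sentence qualifies it: "However, any event may be reported expeditiously to all sites at the discretion of the PI". The same section says that consent will be amended when the event is something current participants should be told.

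The remaining route to all sites is a cumulative Grade 2-5 summary sent with the progress report at continuing review. On its timing, section 11.2 says: "Continuing reviews by the IRB and CT-SRC will occur at least annually".

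Section 10.1.1 makes the sponsor responsible for seeing that SUSAR reports are prepared and "submitted to the appropriate Regulatory Authorities, Competent Authorities, Institutional Review Boards (IRBs) and Ethics Committees (ECs"), in line with the regulations that apply. It sets a 15-day limit for copying the drug supplier. In the other direction, "KARYOPHARM THERAPEUTICS will inform St. Jude regarding any SUSAR detected in other clinical studies".

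**The concern.** An event that is serious, unexpected and at least possibly related (a qualifying event, below) is the kind of signal that another physician treating a child with the same combination would want to hear about soon. Section 10.3 treats it as a leading ground for prompt notice. It then makes the general test whether the event warrants an amendment, which is a different question. A study team cannot tell from the text whether meeting the first criterion is enough.

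Pediatric experience with the combination is small: section 12.3 reports 18 patients enrolled in phase I. Section 11.2 places the protocol in a high-risk monitoring category. Phase II adds four sites, each expected to see about one patient a year, so these sites will learn little from their own cases and depend on what the sponsor sends them.

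**Working it through.** No design figure (power, alpha, sample size) bears on this point. The check is a side-by-side reading, with simple arithmetic for scale.

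**Step 1. Stated routes for a qualifying event.**

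| From and to | Trigger | Time limit | Section |
|---|---|---|---|
| Site to PI | Serious and unexpected | 48-72 hours; 24 hours for an unexpected death | 10.3 |
| To the sponsor's IRB | Serious, unanticipated, related or possibly related | 10 working days | 10.1 |
| Sponsor to drug supplier | SUSAR | 15 days | 10.1.1 |
| Sponsor to all sites, prompt | Generally an amendment; otherwise PI's choice | None stated | 10.3 |
| Sponsor to all sites, summary | All Grade 2-5 events | Continuing review, at least annual | 10.3, 11.2 |

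The inbound route and the routes to the sponsor's IRB and the supplier are mandatory and timed. The prompt outbound route is neither, except that an amendment will generally trigger it.

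**Step 2. Which events fall through.** A qualifying event is left to the summary when all three of these hold: it does not warrant a protocol amendment; it is not information that would lead to a consent amendment; and the PI does not choose to send it. Section 10.3 requires the PI to make a determination, but no outcome of that determination is prescribed for a qualifying event.

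**Step 3. Longest gap.** One continuing-review interval. With review at least once a year, that is at most 12 months. It is shorter if the event falls later in the interval or if reviews are more frequent.

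**Step 4. Section 10.1.1 against 10.3.** Section 10.1.1 refers to the appropriate IRBs and ethics committees and does not name collaborating sites or their investigators. There are two readings:
- If the appropriate bodies include every collaborating site's IRB, 10.3 leaves to the PI something that 10.1.1 makes a sponsor duty.
- If they do not, no section shown requires prompt notice to those IRBs of an event that arose elsewhere.

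The text does not settle which is meant. Either way the two sections need to be read together and aligned.

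**Step 5. SUSARs from other studies.** Section 10.1.1 brings them as far as the sponsor. No section shown says how or when they go on to sites.

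**Step 6. Scale.** The inputs are from section 12.3: 18 phase I patients in 15 months, and four additional sites at one patient each per year.
- The plan's own rate: 18 / 15 = 1.2 per month; 4 / 12 = 0.33 per month; the sum is 1.53, which the plan gives as 1.5.
- Enrollment in 12 months: 1.5 x 12 = 18 patients in all.
- At the additional sites: 4 x 1 = 4 patients. If the event arose at one of those sites, that site already knows, leaving 4 - 1 = 3.

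The documents give no expected rate of qualifying events, so the number of delayed notices cannot be computed.

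**The case against.** The strongest reply is that 10.3 describes triage with a default, not a bar. The default is qualified by the word that opens it, the PI must consider each event, and the PI may send any of them. The amendment trigger is also wide: if enrolled families should be told, consent is amended, and that in turn brings prompt notice to all sites. This stands. A reader might infer that qualifying events go out only when they warrant an amendment, and the documents do not support that. Nor do they show that important events would usually fail the amendment test.

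A reader might also infer that 10.3 conflicts with 10.1.1. That is not shown. Section 10.1.1 places duties on the sponsor and the supplier, is limited to the appropriate bodies under applicable regulations, and sets no duty toward collaborating sites that 10.3 could breach. What remains is an unresolved question of scope.

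It would be too strong to say that supplier SUSARs have no way of reaching sites. Section 5.1 refers to the investigator's brochure and safety updates, and section 11.2 refers to a separate monitoring plan that was not available to check. Either might supply a route.

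Finally, 15 days to the supplier and 12 months to sites concern different recipients, and the 12 months needs several unfavorable circumstances together. Both points stand.

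None of this supplies a requirement. Discretion permits notice without ensuring it, and the mismatch between the first criterion and the default remains in the protocol's own section on the subject.

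**Conclusion.** The point holds as an internal inconsistency and a gap in 10.3. Qualifying events head the list of grounds for prompt notice, yet the default generally reserves prompt notice for amendment-triggering events, and no sentence makes notice to all sites mandatory or timed. Sections 10.1.1 and 10.3 should be reconciled; they are not in open contradiction.

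In size, the text allows a gap of up to 12 months for an event that prompts no amendment and that the PI does not send. About 4 patients at the additional sites (3 if one of those sites was the source), of about 18 overall, would be enrolled in such a year. These counts rest on the plan's accrual assumptions and on review only once a year. They indicate scale and do not predict harm. The conclusion about supplier SUSARs is limited to the documents shown. The change is worth making because it bears on participant safety and costs little.

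**What to change.** In section 10.3:

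1. Replace the default sentence with a requirement along these lines: every event from any site that is serious, unexpected and at least possibly related, and every selinexor SUSAR received from Karyopharm, will be sent to all participating sites, for their IRBs, within one stated limit from the sponsor's awareness. The 15 days already used in 10.1.1 would serve. Sections 10.1 and 10.1.1 give different limits for other recipients, so citing both would not define one.
2. Revise the two sentences that leave to the PI whether an event goes to all sites and whether sites are told to report to their IRBs, so that discretion covers only events outside item 1. Changing the default sentence alone would leave these two contradicting it.
3. Keep the amendment test solely for deciding whether the protocol or consent changes.

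In section 10.1.1, state whether the appropriate IRBs and ethics committees include those of collaborating sites, and cross-refer to 10.3. If the separate monitoring plan already sets a notification rule, cite it and make the wording agree.

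The cost is a short text amendment and a few more notices for sites to file, sent through the existing TRACKS process. The statistical design is unaffected.

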11.0 DATA COLLECTION, MONITORING AND CONFIDENTIALITY

11.1 Data Collection

Electronic case report forms (e-CRFs) will be completed by the clinical trials staff from the Cancer Center Comprehensive Center, Hematological Malignancies Program. Data will be entered from record directly into a secure CRIS database, developed and maintained by St. Jude Clinical Research Informatics.

Data Management will be supervised by the Director of Clinical Trials Management, and Manager of Clinical Research Operations for the Hematological Malignancies Program, working with [name] or his designee. All protocol-specific data and all grade 2-5 adverse events will be recorded by the clinical research associates into the CRIS database, ideally within 2-4 weeks of completion of study phase. All questions will be directed to the attending physician and/or PI and reviewed at regularly-scheduled working meetings. Data collection for adverse events will be captured for 30 days after participant is removed from treatment, or until the participant receives other anti-leukemia therapy.

The attending physicians (or their designees) are responsible for keeping up-to-date roadmaps in the patient's primary SJCRH medical chart. Regular (at least monthly) summaries of toxicity and protocol events will be generated for the PI and the department of Biostatistics to review.

11.2 Study Monitoring

The Clinical Research Monitor will track accrual continuously and verify 100% of all data points on all study participants *quarterly* to assess overall study conduct, Human Subjects Protections, and the accuracy of database entries. Essential regulatory documents and all study documents including medical records, electronic media, database entries, study worksheets, and case report forms will be reviewed for recording and reporting of Adverse Events/Serious Adverse Events (SAEs) to include type, grade, attribution, duration, timeliness and appropriateness. Study documents are also reviewed for participant status, eligibility, the informed consent process, demographics, staging, study objectives, subgroup assignment, treatments, evaluations, responses, participant protocol status, off-study and off-therapy criteria, and for all other specifics as detailed in the protocol. The Monitor will generate a formal report which is shared with the Principal Investigator (PI), study team and the Internal Monitoring Committee (IMC).

Monitoring may be conducted more frequently if deemed necessary by the CPDMO and/or the IMC.

Continuing reviews by the IRB and CT-SRC will occur at least annually. In addition, SAE reports in TRACKS (Total Research and Knowledge System) are reviewed in a timely manner by the IRB/ OHSP.

Source document verification of eligibility for all SJCRH cases will be performed within two weeks of completion of enrollment. This will include verification of appropriate documentation of consent. Monitoring of timeliness of serious adverse event reporting will be done as events are reported in TRACKS.

Monitoring of this protocol is considered to be in the high-risk 2 category (HR-2). The Monitoring Plan is outlined in a separate document from this protocol, but has been submitted for review and approval by the Clinical Trials Scientific Review Committee and the Institutional Review Board.

St. Jude affiliates and domestic collaborating study sites will be monitored on-site by a representative of St. Jude at intervals specified in the Data and Safety Monitoring Plan. International collaborators will be monitored by a Contract Research Organization (CRO), or other mechanisms according to the study-specific monitoring plan.

11.3 Confidentiality

Study numbers will be used in place of an identifier such as a medical record number. No research participant names will be recorded on the data collection forms. The list containing the study number and the medical record number will be maintained in a locked file and will be destroyed after all data have been analyzed.

The medical records of study participants may be reviewed by the St. Jude IRB, FDA, and clinical research monitors.

12.0 STATISTICAL CONSIDERATIONS

The primary objective of the phase I portion of this study is to determine a tolerable combination of selinexor, fludarabine, and cytarabine in patients with relapsed or refractory hematologic malignancies including acute myeloid leukemia (AML), acute lymphoblastic leukemia (ALL), and myelodysplastic syndrome (MDS). Although disease response to treatment will be explored, this phase I portion of the study is not designed to yield a formal evaluation of the efficacy of this regimen.

The primary objective of the phase II portion of the study is to estimate the overall response rate, as defined by complete response or complete response with incomplete count recovery, of selinexor in combination with fludarabine and cytarabine for patients with relapsed or refractory AML. This will be assess be assessing the null hypothesis that overall response rate is $< 30\%$, as specifically described below.

Responsible investigator: [name], PhD
Responsible statistician: [name]

12.1 Dose Escalation Phase

Evaluable for toxicity

Any participant who experiences dose-limiting toxicities (DLT) at any time during the first 35 days after taking the initial dose of selinexor and before receiving non-protocol therapy (such as transplant) is considered evaluable for toxicity. Participants without DLT who receive at least 5 of the 6 prescribed cycle I doses of selinexor and can be followed for 35 days following their initial dose of selinexor are also considered evaluable for toxicity. The evaluation period for purposes of determining whether a participant has a DLT will be the first 35 days following the initial dose of selinexor. Participants who are not evaluable for toxicity (such as those removed early from therapy to start alternate therapy) at a given dose level will be replaced.

Maximum tolerated dose (MTD)

The MTD is empirically defined as the highest dose level at which six participants have been treated with at most one participant experiencing a DLT and the next higher dose has been determined to be too toxic. If the lowest dose level studied is too toxic or the highest dose level studied is considered safe, the MTD will not have been considered estimated.

Dose escalation/de-escalation rules

The rolling-6 design²¹ will be used to determine dose escalation and reduction within each stratum separately. The rolling-6 design is described in greater detail below.

Two to six participants can be concurrently enrolled onto a dose level, dependent on 1) the number of participants enrolled at the current dose level, 2) the number of participants who have experienced DLT at the current dose level, and 3) the number of participants entered but with tolerability data pending at the current dose level. Accrual is suspended when a cohort of six has enrolled or when the study endpoints have been met.

Decision as to which dose level to enroll a participant is based on the number of participants currently enrolled and evaluable, the number of participants experiencing DLT, and the number of participants still at risk of developing a DLT at the time of new participant entry. For example, when three participants are enrolled onto a dose level, if toxicity data is available for all three participants and no DLTs are observed when the 4th participants enter, the dose is escalated and the 4th participants is enrolled to the next higher dose level; if toxicity data is not yet available for one or more of the three participants and no DLT has been observed, or if one DLT has been observed, the new participant is entered at the same dose level; if two or more DLTs have been observed from the three participants, the dose level is de-escalated. This process is repeated for the 5th and 6th participants. Accrual is only suspended when a cohort of six is filled. The starting dose of selinexor will be 30 mg/m²/dose. Table 3 of section 4.3 lists the dose levels to be explored in this study. Section 4.3.2 defines the dose limiting toxicity for this study.

